b.i.d.	bis in diem/twice a day
BMD	Bone mineral density
CI	Confidence interval
BMI	Body mass index
BPQ	Breast pain questionnaire
CBC	Complete blood count
CRF	Case Report/Record Form
DCIS	Ductal carcinoma in situ
ECG	Electrocardiogram
EDL	Enterodiol
ENL	Enterolactone
ER	Estrogen receptor
FDA	Food and Drug Administration
FNA	Fine needle aspiration
FSH	Follicle stimulating hormone
IGF1	Insulin-like growth factor 1
IGFBP3	Insulin-like growth factor binding protein 3
IND	Investigational new drug
i.v.	intravenous(ly)
IRB	Institutional review board
IUD	Intrauterine device
KUCC	University of Kansas Cancer Center
KUMC	University of Kansas Medical Center
LCIS	Lobular carcinoma in situ
LH	Lutenizing hormone
p.o.	per os/by mouth/orally
RPFNA	Random periareolar fine needle aspiration
SAE	Serious adverse event
SDG	Secoisolariciresinol diglycoside
SECO	Secoisolariciresinol
SHBG	Sex hormone binding globulin
SOP	Standard operating procedure

SCHEMA

Initial Screening

Premenopausal women with $\text{BMI} < 40 \text{ kg/m}^2$, age 21-49 who have any of the following risk factors suggesting moderate to increased risk of breast cancer: first or second degree relative diagnosed with breast cancer under the age of 60; prior breast biopsy showing proliferative breast disease, ADH, DCIS, LCIS; multiple biopsies regardless of histology, mammographic density 50% or higher; atypia by RPFNA; BRCA1/2 mutation carrier; 5 yr Gail risk of $\geq 1.67\%$ or 2X risk for age as given in model, or 10 yr Tyrer-Cuzick risk 2x population risk as listed in model.

No pregnancy or lactation for previous 12 months. If using a hormonal type of contraception, should have been using the same type of hormonal contraception for at least 2 months prior to RPFNA.

RPFNA must be able to be scheduled between day 1 and 10 of the menstrual cycle in women having at least 4 menstrual periods in the past year.

If not menstruating because of prior endometrial ablation or use of progestin only IUD or prior hysterectomy with ovaries preserved, must be able to predict timing of follicular phase by hormone levels (estradiol, progesterone, FSH) assessed prior to RPFNA.

If undergoing yearly mammographic screening must have normal mammogram within nine months of RPFNA. If not undergoing routine screening, no mammogram is necessary.

↓

Screening Visit for Eligibility

No flaxseed supplements or antibiotics for the 3 weeks prior to RPFNA.

Random breast FNA performed during follicular phase (Day 1-10) of menstrual cycle or if non-menstruating additional serum aliquot frozen for confirmation of follicular phase.

Serum and plasma specimens frozen for later assays in central laboratories.

CBC and **fasting** metabolic chemistry profile may be performed if desired and study entry anticipated within 3 months of RPFNA

History and physical exam may be performed if desired and study entry anticipated within 3 months of RPFNA

Subject given materials for menstrual diary recording

↓

Tissue Qualifiers for trial participation

Epithelial hyperplasia +/- atypia; Masood score ≥ 13 ; plus Ki-67 $\geq 2\%$

↓

Study Entry Visit (within six months of RPFNA)

History and physical exam (if not performed within 3 months)

Complete BCPT symptom checklist, BPQ Breast Pain Questionnaire and Lignan Diet Questionnaire. Collect Pre-study Menstrual Diary Information

CBC and **fasting** metabolic chemistry profile (if not performed within previous 3 months)

Fasting serum and plasma specimens frozen for later assays in central laboratories.

Spot (+ optional overnight) urine collection and buccal sample for later assays in central laboratories.

Negative urine pregnancy test

Randomization number assigned (next in sequence)

Study Agent dispensed – 6 month supply

Phone contacts at 1 and 3 months to monitor adverse events and concomitant meds

6-month Visit

Review of adverse events and concomitant meds

Return study agent for compliance check; New supply of study agent issued

Phone contact at 9 months to monitor adverse events and concomitant meds

2-4 Weeks Prior to Anticipated Off Study Visit (for non-menstruating women only)

Assess serum hormone levels (Estradiol, Progesterone, FSH); use for prediction of menstrual cycle and scheduling of RPFNA during follicular phase.

12-month Visit (Off-Study)

No antibiotics for the 3 weeks prior to RPFNA.

Fasting blood drawn, preferably within 3-4 hours of last dose of study agent
CBC and metabolic chemistry profile

Serum and plasma specimens frozen for later assays at central laboratories.

Spot (+ optional overnight) urine collection frozen for assay in central laboratories.

Complete BCPT symptom checklist, BPQ Breast Pain Questionnaire, Lignan Diet Questionnaire,
Collect menstrual Diary Information.

Return Study Agent.

RPFNA (Day 1-10 of menstrual cycle); for non-menstruating women, additional serum aliquots
frozen for confirmation of follicular phase.

Phone contact at 2 weeks off study agent to monitor adverse events

1.0 OBJECTIVES

The overall objective is to determine whether the natural flaxseed lignan, secoisolariciresinol diglycoside (SDG), in amounts providing plasma lignan levels associated with reduced breast cancer risk, will favorably modulate risk biomarkers for breast cancer development. This will provide biologic evidence of SDG's potential for breast cancer chemoprevention. Based on a positive pilot study in which both Ki-67 and the proportion of women with atypical cytomorphology was reduced with 12 months of SDG 50 mg/day, a randomized, placebo-controlled clinical chemoprevention trial will be conducted wherein pre-menopausal women at increased risk for the development of breast cancer will receive Brevail® (200 mg, equivalent to 50 mg of SDG) or matched, blinded placebo for 12 months. A total of 242 subjects will be accrued, randomized 2:1 to SDG vs placebo, with the goal of achieving 220 subjects completing study and evaluable for biomarker change.

The primary objective is to determine if women randomized to 12 months of SDG exhibit greater change in the proportion of breast epithelial cells expressing the proliferation marker Ki-67/MIB-1 in hyperplastic benign breast tissue than do women randomized to placebo.

Secondary objectives are:

- 1) to determine if 12 months of SDG is associated with favorable modulation of other risk biomarkers including cytologic atypia, and serum levels of bioavailable estradiol and testosterone, IGF-I:IGFBP-3 ratio, c-peptide, adiponectin, and leptin.
- 2) to determine if Ki-67 and modulation of other risk biomarkers is correlated with change in blood or urine lignans.
- 3) to determine impact or potential impact on quality of life as measured by the BPQ breast pain questionnaire (a modified McGill Pain questionnaire), The Breast Cancer Prevention Trial (BCPT) Symptom Checklist a menstrual diary for cyclicity and cycle length for women not on cycle modulating contraceptives; and antimullerian hormone (AMH), a measure of follicular reserve.

An exploratory objective is to interrogate SDG's mechanism of action through measurement of changes in hormones, growth factors, gene expression, adipokines and cytokines and proteomic signatures.

The overriding hypothesis is that biomarkers assessed both in serum and in hyperplastic breast tissue obtained by RPFNA from high risk pre-menopausal women will be favorably modulated by 12 months of SDG without negatively affecting quality of life.

Specifically, it is hypothesized that SDG administration will be associated with

- a reduction in proliferation as measured by Ki-67;
- a reduction in proportion of specimens with cytologic evidence of atypia;
- a favorable tolerability and quality of life profile;
- no significant impact on menstrual cycle length;
- no significant effect on follicular reserves as measured by early follicular phase anti-mullerian hormone in women entering the study between ages 21-35;
- a reduction in breast pain in those women entering the study with mastalgia.

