2.4.4.2. Change in Ki-67 and cytomorphology

Thirty-six (80%) of the 45 evaluable subjects demonstrated a decrease in Ki-67, from a median of 4% (range 2-16.8%) to 2% (range 0-15.2%) ($p<0.001$ by Wilcoxon signed rank test). A decrease from baseline in the proportion of women with atypical cytology from 62% to 42% ($p=0.035$) was also observed.

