4.4 Inclusion Criteria for Study Entry

- 4.4.1 RPFNA performed within 6 months of the Study Entry Visit and in the follicular portion (day 1-10) of the menstrual cycle. Note that day 1 is defined as the first day of bleeding. For non-menstruating women, RPFNA during the follicular phase must be confirmed by hormone levels drawn on the day of RPFNA. Either clinical laboratory results are sent to Protocol Chair for assessment of menstrual cycle phase; or an additional frozen serum aliquot is sent to KUMC for assay of hormone levels and phase confirmation. Confirmation of follicular phase will be included in the eligibility report for the potential subject.
- 4.4.2 RPFNA specimen exhibits hyperplasia +/- atypia; Masood score of ≥ 13 with ≥ 500 cells on the cytology slide.
- 4.4.3 Ki-67 $\geq 2\%$ positivity (≥ 500 cells).
- 4.4.4 Willing to continue on the same or similar type of contraception during the 12 month course of study. If using non-hormonal contraception, continue that and if hormonal contraception continue that. If heterosexually active, must be agreeable to use some form of contraception during the trial unless husband or partner has had a vasectomy or subject has had uterus removed. Safety of SDG during pregnancy has not been documented.
- 4.4.5 Have reasonable organ function as documented by CBC and metabolic chemistry profile (within 3 months prior to Study Entry Visit).
- 4.4.6 Willing to undergo a history and physical at baseline and 12 months and be contacted periodically by the trial coordinator during the 12 month study period.
- 4.4.7 Willing to repeat RPFNA at 12 months following initiation of study agent.
- 4.4.8 Willing to have blood drawn at baseline and 12 months. If non-menstruating, an additional draw will be performed at approximately 11 months so as to predict when to perform the RPFNA
- 4.4.9 Able to understand and willing to provide informed consent for the RPFNA's and study participation.

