11.2 Statistical Analysis

All analyses will be intent-to-treat. All subjects randomized will be evaluable for safety and all subjects that have both a pre and post specimen are evaluable for efficacy. Primary analysis of efficacy will be performed on all evaluable subjects and secondary analysis will be done on those subjects who received at least 6 months of study medication and were confirmed as being in the follicular phase for both RPFNA procedures. From our experience we have very little missing data; however, if the missing data rate is above 5%, we will use multiple imputation to impute these values to perform the primary and secondary analyses.

The primary outcome will be change in Ki-67 (percent of cells expressing Ki-67) from baseline to 12 months. The two-sample t-test will be used to compare the change in Ki-67 between the SDG

and placebo groups. Any difference in baseline values of Ki-67 between the two groups would be due to chance, however, if there is a significant difference, then analysis of covariance adjusting for baseline values will be performed. Due to potential skewness in these variables we will assess whether or not the Central Limit Theorem may be assumed. Given the sample size the existence of an extremely high degree of skewness would require the use of the Wilcoxon Signed Rank test.

For the secondary endpoints, similar methods as above will be used to compare the treatment and control groups at two time points for all markers, i.e., serum hormones and clinical laboratory tests. We will also correlate change in the primary biomarker Ki-67 with change in other markers (e.g., bioavailable estradiol, cytokines, RTqPCR results) using Pearson's correlation coefficient. Again, if there exists a high degree of skewness in these variables, Spearman's correlation will be utilized.

Multiple regression analysis will also be used to investigate whether changes in Ki-67 are due to variables other than treatment effect (e.g., age, cytromorphology, Gail risk; as well as the predictive effect of other biomarkers on modulation of Ki-67). Best subsets and stepwise approaches will be employed while controlling for treatment group.

For comparison of moderate or worse toxicities we will consider grade 3 toxicity or premature trial discontinuation as the critical events. The prevalence of events in the SDG vs. the placebo arm will be examined by Fisher's exact test.

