5.1 Breast Tissue Cytomorphology

Two slides are made from each pooled sample by a liquid-based technique (ThinPrep®): two for cytomorphology under RNAse-free conditions one of which will undergo microdissection, processing to RNA and then cDNA and frozen at -80°C until later use for RT-qPCR. Remaining cells will be left in PreservCyt® for later use for RT-qPCR. Initial cytomorphologic assessment is performed by the cytotech and then the slide is photographed and sent to the cytopathologist, [name] for final assessment. Slides will be given both a categorical classifier (non-proliferative or normal, hyperplasia, hyperplasia borderline atypia, atypical hyperplasia, or suspicious for cancer) and a Masood Index score [106]. The Masood score is the result of 1-4 points given for 6 different morphologic characteristics: cellular arrangement (monolayer, overlapping nuclei, clustering, loss of cohesion), pleomorphism, myoepithelial cells (many, moderate, few, absent); anisonucleosis (absent, mild, moderate, conspicuous); nucleoli (absent, micronucleoli, micro and rare macronucleoli, predominately macronuclei); and chromatin clumping (absent, rare, occasional, frequent). Change in Masood score will be assessed by subtracting the off-study score from the baseline score

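### The Masood cytology score is recorded and its change is to be assessed, but it has no hypothesis and by default gets a change-score t-test; a baseline-adjusted comparison should be named beside the atypia proportion

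*Combined protocol and SAP*

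**What the plan says.** Section 1.0 (Objectives) lists the secondary biomarkers under "favorable modulation of other risk biomarkers including cytologic atypia", so cytology comes first. The matching hypothesis in the same section is "a reduction in proportion of specimens with cytologic evidence of atypia". No other cytology hypothesis is stated.

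Appendix 1, section 5.1 gives each slide two readings. One is a category: "non-proliferative or normal, hyperplasia, hyperplasia borderline atypia, atypical hyperplasia, or suspicious for cancer". The other is a numeric index: "The Masood score is the result of 1-4 points given for 6 different morphologic characteristics". The appendix adds: "Change in Masood score will be assessed by subtracting the off-study score from the baseline score".

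Section 11.2 does not name cytology as an endpoint. For secondary endpoints it says that "similar methods as above will be used to compare the treatment and control groups at two time points for all markers", and its examples are serum hormones and laboratory tests. The methods referred to are those for Ki-67: a two-sample t-test on change, analysis of covariance if baseline values differ significantly, and a rank test under extreme skewness. Cytomorphology otherwise appears only as an explanatory variable in the Ki-67 regression. The one test suited to proportions, Fisher's exact test, is assigned to toxicity.

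**The concern.** The plan sets up two cytology measures and connects them poorly. The atypia proportion has a hypothesis but no named test. The Masood score has a planned change calculation but no hypothesis, and a test only by inference from general wording. The plan does not say which result answers the cytology question. All secondary analyses are tested at a two-sided 5% without multiplicity control, so the choice could be made after the results are known.

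The default for the score is also inefficient. A change-score t-test subtracts the whole baseline value, although baseline and 12-month scores are unlikely to be perfectly correlated. Making adjustment depend on a significant baseline difference means that it will usually not be used.

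Section 2.4.2 describes atypia as a strong risk marker, set aside as the primary endpoint for reasons of enrolment and generalizability. Cytology is therefore the main tissue evidence alongside Ki-67, and its analysis should be stated and reasonably efficient.

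**Working it through.** **The plan's own figure.** The only stated power is for Ki-67: 220 evaluable, 2:1, difference 2.5, SD 6, two-sided 5%. The standard error is 6 × √(1/73.33 + 1/146.67) = 0.858. Then 2.5/0.858 = 2.913 and 2.913 − 1.960 = 0.953, giving power of 83.0%. The stated 83% reproduces. No power is given for cytology, so what follows rests on labelled assumptions.

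**Inputs from the documents.** The Masood range is 6 × 1 to 6 × 4, that is 6 to 24. Entry criterion 4.4.2 requires "RPFNA specimen exhibits hyperplasia +/- atypia; Masood score of" at least 13, so baseline runs from 13 to 24. Pilot atypia was 62% at baseline and 42% at 12 months in 45 women, without a control arm (2.4.4.2). The Masood SD, its pre-post correlation and its correlation with the atypia call are not given.

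**Step 1: covariate adjustment against the change-score t-test.** Assume equal variance σ² at both visits and pre-post correlation r.

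- Variance of change: 2(1 − r)σ².
- Residual variance adjusted for baseline: (1 − r²)σ².
- Ratio: (1 − r²)/[2(1 − r)] = (1 + r)/2.

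| Assumed r | Change | Adjusted | Ratio | Reduction |
|---|---|---|---|---|
| 0.3 | 1.40σ² | 0.91σ² | 0.65 | 35% |
| 0.6 | 0.80σ² | 0.64σ² | 0.80 | 20% |

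This is like running the change-score test on 220/0.80 = 275 to 220/0.65 = 338 women.

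**Step 2: the entry floor.** Selection on the baseline score leaves the regression slope and residual variance as they were, but shrinks baseline variance to a fraction v. The ratio becomes (1 + r)/[(1 + r) + (1 − r)v]. If v were 0.7 (an assumption), r = 0.3 gives 1.3/1.79 = 0.73 and r = 0.6 gives 1.6/1.88 = 0.85. The reduction is then 15-27% instead of 20-35%. The adjusted analysis still has the smaller residual variance.

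**Step 3: illustrative power.** Simulation with 147 vs 73 women, 42% atypia on SDG and 57% on placebo at 12 months, an integer score and r of 0.3-0.6:

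| Correlation of Masood with the scale behind the atypia call | Change-score t-test | Baseline-adjusted score |
|---|---|---|
| 1.0 | 62-82% | 77-88% |
| 0.9 | 50-64% | 66-74% |

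**Step 4: score against yes/no.** If atypia were a cut on the same normal scale as the score, the yes/no outcome would have relative efficiency φ(z)²/[p(1 − p)]: 0.627 at p = 0.42, 0.636 at 0.52 and 0.615 at 0.62. The loss is 36-38%. If the score correlates c with that scale and the drug acts through it, the score's own efficiency is about c². The two are equal where c² = 0.615 to 0.636, that is c = 0.78 to 0.80. Below that, the yes/no form is the better one.

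**Step 5: category against yes/no.** Under several assumed splits across the categories, the yes/no cut lost 4-27% relative to the ordered category, less than a third in every split tried.

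**The case against.** A reader might infer that the graded cytology information is thrown away. The documents do not support that. Appendix 1, section 5.1 plans to assess Masood change, and the general methods of 11.2 fit a numeric change better than they fit a proportion. The hypothesis in 1.0 states an expected direction; it does not say that the proportion is the only cytology analysis.

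A reader might also infer that over a third of the information is lost. That figure requires atypia to be a threshold on the scale that Masood measures. Section 5.1 presents the category and the index as separate readings and defines neither from the other. Step 4 shows how quickly the advantage disappears.

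The yes/no form has a substantive reason as well. The fivefold risk in 2.4.2 relates to cytologic atypia, and the documents give no risk evidence for Masood movement within hyperplasia. Demoting the proportion would exchange interpretability for an uncertain gain in power.

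These objections stand, and the point is limited accordingly. They do not answer the remaining gap. The score still has no declared role, its default test is less efficient than the simple alternative, and 11.2 gives no test for the stated proportion.

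**Conclusion.** The point holds as a modest one on a secondary endpoint. The stated cytology hypothesis is a proportion, and the Masood score, though planned for assessment, has no hypothesis and only a default change-score t-test.

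The firmer gain is from covariate adjustment: residual variance 20-35% lower for r of 0.3-0.6 with equal variances, and somewhat less if the entry floor narrows the baseline spread. Both r and the spread are assumptions. The power figures are illustrative, because the 42% comes from an uncontrolled pilot and the placebo rate is assumed.

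The gain over the yes/no outcome cannot be fixed from the documents. The 36-38% is an upper figure under the shared-scale model, and the advantage is about gone at a correlation near 0.8. The documents therefore do not support replacing the atypia proportion.

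**What to change.** In 11.2, before cytology is looked at by arm:

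- Name a between-arm comparison of the 12-month Masood score, with baseline Masood score as covariate, as a pre-specified cytology analysis. Make the adjustment unconditional. A proportional-odds model on the five-level category with baseline category as covariate is an acceptable alternative; choose one.
- Keep the proportion with atypia in each arm, and report the between-arm difference with a confidence interval. Say which of the five categories count as atypia, since one of them is borderline.
- Add the chosen graded measure to the cytology hypothesis in 1.0, so that the objective, Appendix 1 and 11.2 agree.

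The cost is a change of wording and one more pre-specified secondary analysis in a plan that does not control multiplicity among secondary endpoints. The scores are already collected. The primary Ki-67 analysis and the sample size do not change.

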11.1 Sample Size and Power

The primary outcome of interest is efficacy of SDG relative to the placebo, thus the pre- to post-treatment change in a proliferation index (percent of cells expressing Ki-67) is the basis of the power analyses. From our pilot study, the average percentage of cells expressing Ki-67 at baseline was 4%, and the average change in percent of cells expressing Ki-67 was a 2.4% reduction, for subjects meeting similar eligibility requirements as used in this trial.

A 2:1 randomization of 220 evaluable subjects will provide 83% power to detect a 2.5% reduction in Ki-67 for the treatment group compared to no reduction in the control group; this will be our primary endpoint. This is based on an assumption of a common standard deviation of 6% for change in Ki-67 in both groups and a Type I error rate of 5%. Within the target of 220 evaluable subjects, we expect to recruit 72 women taking oral contraceptives (OC) and 148 women not taking OCs. Because the efficacy of SDG is unknown for OC users, we considered different scenarios and evaluated the average effect in the SDG arm and the corresponding power. For 0-70% efficacy of SDG among OC users, the respective average Ki-67 reduction range from 1.7% to 2.3% will result in a statistical power ranging from 50% to 76%.

Ki-67 reduction in SDG arm (non-OC)	Efficacy of SDG in OC	Ki-67 reduction in SDG arm (OC)	Ki-67 reduction in SDG arm (OC & non-OC avg.)	Power
2.5%	0%	0%	1.7%	50%
2.5%	20%	0.5%	1.8%	55%
2.5%	50%	1.3%	2.1%	68%
2.5%	70%	1.8%	2.3%	76%
2.5%	100%	2.5%	2.5%	83%

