Evaluation of agent-induced hormonal changes - We will examine whether SDG has any effects on serum levels of bioavailable estradiol, and testosterone, determined at baseline and after 12 months of study medication. We will determine whether addition of SDG alters the frequency or length of menstrual cycles. Effects on follicular reserve will be evaluated with anti-mullerian hormone in a sub-cohort of pre-menopausal women between ages 21 and 35 at study entry. Antimullerian hormone (AMH) is one of the earliest and most sensitive measures of follicular reserve declines for approximately 10 years before the cessation of menses. A distinct advantage for trial purposes is that it does not vary with day of menstrual cycle [119].

Adverse Events and Quality of Life – Change from baseline to 12 months will be assessed for mastalgia (expected in 30-50% of subjects at baseline), menstrual cycle and follicular reserve, and quality of life, as a function of SDG intake, plasma lignan levels and urinary lignan excretion. We will use the breast pain questionnaire (BPQ), which is a modified short form of the McGill Pain questionnaire (SF-MPQ) to assess breast discomfort and the Breast Cancer Prevention Trials (BCPT) Symptom Checklist to monitor quality of life

Correlative analyses will be performed with plasma and urine ENL and total lignans as the independent variable, with modifying variables of baseline BMI age and specific SNPs such as CYP17.

Since this is a phase IIB trial, the power and sample size for the primary endpoint was determined with a two-sided type I error rate of 5%. All subsequent secondary, tertiary and exploratory analyses will also be tested with a two-sided type I error rate of 5%. This may result in an elevated false positive rate for these secondary and tertiary analyses, however, since this is a Phase IIB study, we felt to control the type I error rate for the secondary, tertiary and exploratory analyses would be too conservative.

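### The hypotheses of no effect on follicular reserve and cycle length are paired only with 5% difference tests, so a non-significant result, likeliest in the AMH sub-cohort, would appear to confirm them

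*Combined protocol and SAP*

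**What the plan says.** The list of specific hypotheses in section 1.0 contains two statements of no effect. One is "no significant effect on follicular reserves as measured by early follicular phase anti-mullerian hormone in women entering the study between ages 21-35". The other is "no significant impact on menstrual cycle length".

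Section 11.2 (Statistical Analysis) takes up both outcomes in neutral terms. For AMH: "Effects on follicular reserve will be evaluated with anti-mullerian hormone in a sub-cohort of pre-menopausal women between ages 21 and 35 at study entry". For the cycle: "We will determine whether addition of SDG alters the frequency or length of menstrual cycles". The primary method is a difference test ("The two-sample t-test will be used to compare the change in Ki-67 between the SDG" and placebo groups), and the same section carries similar methods over to the secondary endpoints. It also relates change in menstrual cycle and follicular reserve to SDG intake and to plasma and urinary lignans. The error rate is set for everything at once: "All subsequent secondary, tertiary and exploratory analyses will also be tested with a two-sided type I error rate of 5"%.

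The populations differ. AMH is restricted to women aged 21-35 at entry, and their number is not given. Cycle length is assessed by "a menstrual diary for cyclicity and cycle length for women not on cycle modulating contraceptives", and section 11.1 states: "Within the target of 220 evaluable subjects, we expect to recruit 72 women taking oral contraceptives (OC) and 148 women not taking OCs".

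**The concern.** A difference test can give evidence that an effect exists. Failing to reject does not give evidence that it is absent. When the hypothesis is itself worded as the absence of a significant effect and the only tool is a two-sided 5% test, p>0.05 satisfies the hypothesis as written. The incentive then runs the wrong way: a smaller or noisier sample makes the reassuring conclusion easier to reach.

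Section 11.2 discusses the raised false-positive rate from leaving the secondary analyses unadjusted. For these two hypotheses the error that matters is the false negative, and the plan does not discuss it.

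The outcomes are not incidental. Section 3.0 counts surrogate markers of fertility among the considerations important for uptake, section 2.1 looks for an agent safe enough to need no medical monitoring, and section 2.4.4.5 reports irregular menses in 26% of pilot subjects. A statement of no significant effect on follicular reserve in healthy young women would carry weight even if the data could not exclude a sizeable loss.

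**Working it through.** **Inputs from the documents.** 220 evaluable women, 2:1 allocation, Ki-67 difference 2.5, SD 6, type I error 5%, power 83% (11.1); two-sided (11.2). Entry age 21-49 (4.2.1). Pilot median age 43 (2.4.4). 148 evaluable women expected not to be on oral contraceptives (11.1).

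**Assumptions.** The AMH sub-cohort is 15%, 20%, 30% or 40% of 220, that is 33, 44, 66 or 88 women. The illustrative true difference is 0.5 SD of the change score. The documents give neither a sub-cohort size nor any SD for AMH or cycle length.

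**Step 1: the plan's own figure.** With 147 vs 73 women, the standard error in SD units is √(1/147 + 1/73) = 0.143. The standardized effect is 2.5/6 = 0.417, so the noncentrality is 0.417/0.143 = 2.91. Noncentral-t power is 82.6%, and the normal approximation gives 83.0%. The stated 83% reproduces, but it covers Ki-67 only.

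**Step 2: AMH.** For arms n1 and n2, SE = √(1/n1 + 1/n2), noncentrality = 0.5/SE, and 95% CI half-width = t(0.975, n1+n2−2) × SE, all in SD of change. For 22 vs 11: SE = 0.369, noncentrality = 1.35, half-width = 2.04 × 0.369 = 0.75.

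| Women (SDG/placebo) | Power at 0.5 SD | Chance of p>0.05 | CI half-width |
|---|---|---|---|
| 33 (22/11) | 26% | 74% | 0.75 SD |
| 44 (29/15) | 34% | 66% | 0.64 SD |
| 66 (44/22) | 47% | 53% | 0.52 SD |
| 88 (59/29) | 59% | 41% | 0.45 SD |

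**Step 3: sensitivity to the meaning of SD.** If the 0.5 SD is in between-woman SD of AMH, then SD of change = between-woman SD × √(2(1−r)), where r is the pre-post correlation. The table then holds at r = 0.5. At r = 0.8 (assumed; the documents give no r), the effect is 0.5/√0.4 = 0.79 SD of change. Power is then 55%, 68%, 85% and 93%, so the chance of p>0.05 falls to 45%, 32%, 15% and 7%.

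**Step 4: cycle length.** With 148 women (99 vs 49), SE = 0.175 and the CI half-width is 0.35 SD. Power is 81% at 0.5 SD and 40% at 0.3 SD. The 148 is an upper guide, since users of non-oral hormonal methods and non-menstruating women would reduce it.

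**The case against.** The strongest reply is that the plan never says p>0.05 will be reported as no effect. Section 11.2 says that AMH effects will be evaluated and asks whether SDG alters the cycle, and the secondary objective in 1.0 speaks of determining impact. A 5% level commits nobody to misreading a null result. This is right as far as it goes: the rule is implied by putting 1.0 beside 11.2, not stated. It does not remove the point, because the plan gives no other criterion by which those hypotheses could be judged.

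A second reply is that the plan has more than two-arm tests, since it also relates these outcomes to lignan exposure and names age as a modifying variable in the correlative analyses. That is true, but those analyses fall under the same 5% rule and also cannot establish absence of an effect.

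A third is that the size of the problem rests on assumptions. This stands. The sub-cohort share and the 0.5 SD are not in the documents, and a high pre-post correlation would improve the picture considerably.

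A reader might also infer that both outcomes suffer from a small sub-cohort. The documents do not support that for cycle length, whose population is larger and not restricted to ages 21-35. Nor do they support the inference that the trial must set an equivalence margin or recruit more women: the defect lies in how a null result may be interpreted, and estimation addresses that.

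**Conclusion.** The point holds as a mismatch between the wording of two hypotheses and the only inferential criterion supplied. For AMH it has practical consequences. An entry range of 21-49 and a pilot median of 43 make a minority aged 21-35 likely, although admitting oral contraceptive users could lower the age mix. Across the assumed 15-40% share, the plan would often return a non-significant result despite a half-SD change-score difference, with intervals too wide to reassure. The exact frequencies depend on the effect scale and on a correlation that the documents do not give. They should be read as a range of scenarios, not as a forecast. For cycle length, precision may be adequate for moderate effects, and the weakness is chiefly the wording. Both are secondary outcomes of a phase IIB trial, so this should be corrected but does not threaten the primary Ki-67 comparison.

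**What to change.** In the hypotheses of section 1.0, replace the two statements of no significant effect or impact with the aim of estimating the effect of SDG on AMH (ages 21-35) and on cycle length.

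In section 11.2, add the following:
- The between-arm difference in 12-month AMH, on the log scale if skewed, will be reported with a 95% CI, adjusted for baseline AMH and age.
- The between-arm difference in cycle length will be reported with a 95% CI, adjusted for the baseline value.
- A p-value above 0.05 will not be reported as absence of effect for either outcome.
- The largest AMH loss that the interval does not exclude will be stated.

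The cost is a change of wording and reporting, with no margin, extra women, samples or visits. What is given up is the option of claiming no effect from a non-significant p-value.
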